10.1.2. Time to Event Analysis

A Cox's proportional hazards regression model will be performed. The model will include demographic and preoperative/operative characteristics (including but not limited to age class, gender, concomitant procedures, and surgical approach). Hazard rates (90% CI) will be reported. The assumptions of proportionality will also be investigated with a time-dependent exploratory variable. In case of non-proportional hazards, a Weibull model will be assumed as parametric form of the distribution of survival times.

The following mortality and morbidity events will be evaluated by time-to-event analysis:

- death
- reoperation
- structural valve deterioration
- moderate or severe valve regurgitation
- valve endocarditis
- valve thrombosis
- thromboembolic events
- hemolysis
- major bleeding

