2.3 SAMPLE SIZE CALCULATION

A sufficient number of subjects will be enrolled in this study to allow a minimum of 75 evaluable CT scans for the primary endpoint. Evaluable scans are those where a determination of normal or abnormal leaflet motion is possible. Considering an attrition rate of 15% of subjects, the sample size targeted for enrollment is approximately 88 subjects.

A sample size of 75 evaluable CT scans produces an Exact two-sided 90% CI with a width lower than 13% when the sample proportion is lower than 10% (evaluation calculated using PASS software, version 13).

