5.1 GENERAL PRINCIPLES

The statistical analysis will be performed on the analysis study database with SAS version 9.4 or above (SAS Institute, Cary, N.C.).

If two or more of the analysis sets as defined in Section 6 coincide or the difference is less than 5%, presentations will only be prepared for the population less restrictive.

The default significant level will be 10%. Confidence Intervals (CIs) will be calculated at 90% confidence level and all tests will be two-sided, unless otherwise specified in the description of the analyses.

All the data collected and derived in the study will be presented in subject data listings.

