5.2 DESCRIPTIVE STATISTICS

Descriptive statistics will be calculated using as reference the number of subjects in the relevant analysis population (any exception will be specified) according to the nature of the data as follows:

Study: APR002 BELIEVE

- Continuous variables: number of non-missing observations, arithmetic mean, standard deviation, minimum and maximum values, median and quartiles.
 - If there are less than 5 observations, only the number of non-missing observations, arithmetic mean, median, minimum and maximum will be presented.
- Categorical variables: number of non-missing observations (n), the number of missing and the relevant percentage on the analysis population, number and relative frequencies. If not defined otherwise, the percentage denominator will be the number of subjects with nonmissing information.
 - In case of subcategories, the relative frequencies will be calculated based on the subjects in the subcategory, in this case a footnote will be added explaining the different denominators.
- Time-to-event variables: number of non-missing observations (n), minimum, first quartile, median including 90% CI, third quartile, and maximum. For calculating the survival estimate 90% CI bounds the log-log transformed estimate of CI bounds will be used. Greenwood formula will be used to estimate the variance of the log-log transformation of the Kaplan-Maier estimator.

In addition, Kaplan-Meier estimates and plots will be provided with:

- o the respective number at risk and the Kaplan-Meier estimates at time points 1 month, 3 months, 6 months, 9 months and 1 year.
- o the median and its 90% Cl.
- o the Hazard Ratio (HR), its 90% CI and the relevant p-value, when applicable.

Subjects ongoing and who are free from event at the analysis cut-off date will be censored at the analysis cut-off date. Subjects who have discontinued without an event will be censored at the date of discontinuation.

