11.5 Freedom from Valve Safety

The following mortality and morbidity outcomes will be analyzed by means of time to event methods:

all-cause mortality

COPYRIGHT LIVANOVA. ALL RIGHTS RESERVED. MAY NOT BE REPRODUCED WITHOUT PERMISSION. ALL HARD COPIES SHOULD BE CHECKED AGAINST THE CURRENT ELECTRONIC VERSION WITHIN MASTERCONTROL PRIOR TO USE AND DESTROYED PROMPTLY THEREAFTER. ALL HARD COPIES ARE CONSIDERED UNCONTROLLED DOCUMENTS.

LN-GLB-CLN-TEM-0033 rev1 Page 21 of 42

- valve re-intervention
- myocardial infarction
- structural valve deterioration
- moderate or severe valve regurgitation
- valve endocarditis
- valve thrombosis
- thromboembolic events
- hemolysis
- major bleeding
- pacemaker implantation

Cox's proportional hazards regression models (Cox 1972, Breslow 1975) will be performed including, one by one, the following covariates: age class [refers to "≥18 and <65" years], gender [refers to "male"], ethnicity [refers to "not Hispanic or Latino"], presence of subject risk factor at baseline [refers to "No"], , NYHA at baseline [refers to "Class I"], abnormality of ascending aorta or of aortic root at implant [refers to "No"], presence of aortic regurgitation measured by post-implant intraoperative TEE [refers to "No"], reduced leaflet motion at first CT scan [refers to "No"], including the subgroup defined in Section 5.3: concomitant procedures [refers to "without"], subject symptoms [refers to "asymptomatic"], ACT/DATP [refers to "off"], Core Lab evaluation [refers to "TEE"].

Study: APR002 BELIEVE

Hazard rate, and its 90% CI, will be reported for each covariate.

Proportional hazard assumption will be investigated for each time-dependent outcome. In case of non-proportional hazards, a Weibull model will be assumed as parametric form of the distribution of survival times.

An additional analysis will be performed in order to evaluate the time free from ACT/DAPT to primary endpoint (reduced leaflet motion) up 1 year post-implant. Kaplan-Meier estimates and plots of time to event after implant will be produced as in Section 5.2. Subjects will be included in the analysis starting from their stop date of ACT/DAPT until the first evaluation of leaflet motion.

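### The Weibull fallback for non-proportional hazards does not, in its standard form, relax the proportionality assumption that triggers it

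*SAP*

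**What the plan says.** SAP 11.5 lists eleven mortality and morbidity outcomes for time-to-event analysis. It states that "Cox's proportional hazards regression models (Cox 1972, Breslow 1975) will be performed including, one by one, the following covariates", and then lists baseline, implant and post-implant covariates, including reduced leaflet motion at the first CT and the SAP 5.3 subgroups. For reporting it says "Hazard rate, and its 90% CI, will be reported for each covariate"; in a Cox model that can only mean a hazard ratio.

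On the model assumption it says "Proportional hazard assumption will be investigated for each time-dependent outcome", without naming a test or threshold. The response to a failed check is one sentence: "In case of non-proportional hazards, a Weibull model will be assumed as parametric form of the distribution of survival times".

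Protocol 10.1.2 contains the same Weibull sentence. It adds one detail on the check: "The assumptions of proportionality will also be investigated with a time-dependent exploratory variable". That variable is a diagnostic and is not carried into the fallback.

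Elsewhere, SAP 5.2 provides for "the Hazard Ratio (HR), its 90% CI and the relevant p-value, when applicable" beside the Kaplan-Meier output, and SAP 5.1 sets the level: "Confidence Intervals (CIs) will be calculated at 90% confidence level and all tests will be two-sided".

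**The concern.** A fallback should drop the assumption that failed. Cox regression leaves the baseline hazard free and assumes that the ratio between covariate levels is constant over time. A common-shape Weibull regression keeps the constant ratio and also fixes the form of the baseline hazard. It is more restrictive than the model it replaces, and in the wrong place.

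The situation is foreseeable. A risk factor may act differently in the weeks after valve surgery than later in the year, and the plan itself treats day 30 as a boundary when it computes linearized rates (protocol 10.1.4, SAP 13.1.2). If the check detects such a pattern, a report could state that non-proportionality was found and handled when the handling changed nothing of substance. An averaged ratio may describe neither period.

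**Working it through.** **1. The plan's own figures.** The documents give no power, event count or hazard ratio for these models, so there is no planned figure to reproduce for them. The only design figure is the exact 90% interval at n = 75 (SAP 2.3). At 7/75 = 9.3%, the largest attainable proportion below 10%, the Clopper-Pearson width is 0.1235, below 13% as stated. Enrollment of 75/0.85 = 88.2 agrees with the stated figure of approximately 88. These figures serve only to set the scale of the trial.

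**2. Algebra.** With covariate x, common shape k and scale parameter λ, the Weibull hazard is

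h(t | x) = k · λ · t^(k−1) · exp(b·x).

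The ratio of x = 1 to x = 0 is exp(b), because t cancels. With k = 1.7 and b = 0.8 the ratio is 2.2255 at t = 0.05, 0.25, 0.5 and 1.0 year. An acceleration factor would be exp(b/k) in size: another single number, and a one-to-one transform of the hazard ratio once k is given.

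**3. Large-sample illustration around day 30.** Assumptions, not from the documents: 400,000 subjects in two equal groups; reference-group cumulative hazard 3% to day 30 and 6% from day 30 to day 365; censoring at day 365.

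| True HR to day 30 | True HR after | Cox HR | Weibull HR |
|---|---|---|---|
| 3.0 | 0.5 | 1.36 | 1.36 |
| 4.0 | 1.0 | 2.02 | 2.03 |

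The fallback moves the estimate by less than 1%. In the first row, a covariate that halves late risk is shown as raising risk overall, both before and after the remedy.

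**4. A second set of assumptions.** Reference hazard 0.3 per year, true HR 4.0 before 0.25 year and 0.5 afterwards, censoring at 1 year.

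- n = 20,000: Cox 1.525, Weibull 1.527.
- 400 simulated studies of n = 88 (mean 26 events): median HR 1.48 from both models, correlation of log HRs 0.9996, largest difference in log HR 0.041 (a factor of exp(0.041) = 1.04).
- Letting the shape depend on the covariate (n = 20,000) gave shapes 0.99 and 0.56 and an HR falling from 2.97 at 0.05 year to 0.82 at 1 year, with a likelihood-ratio gain of 491 on 1 df. A Weibull model that relaxes proportionality therefore exists, but it has to be specified.

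**5. How often it would matter here.** Protocol 2.3.1 gives pooled rates for earlier studies of this valve. If they carried over to 88 subjects (an assumption; the late rates have no stated horizon):

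- early deaths 0.034 × 88 = 3.0; late deaths 0.070 × 88 = 6.2
- early strokes 0.012 × 88 = 1.1; late strokes 0.008 × 88 = 0.7
- no valve thrombosis or structural deterioration was reported

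With 88 subjects under the step 3 hazards, mean events are 9 to 11. A period-by-covariate likelihood-ratio test at the 0.10 level rejects in about 42% of trials (3.0/0.5) and 35% (4.0/1.0). Both groups have events in both periods in about 45% and 61% of trials. At stroke-like rates there are about 3 events, rejection is about 15%, and all four cells are filled in only 1 to 3% of trials.

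**The case against.** The strongest reply is that the text does not fix the implementation. It names a Weibull distribution of survival times and does not say that the covariate acts on the scale only, that groups share a shape, or which measure is reported. Separate fits per group, or a covariate-dependent shape, would allow non-proportional hazards. This stands in part. A reader might infer that the plan commits itself to reporting the same misleading ratio. The documents do not support that, because the sentence on reporting a hazard rate comes before the fallback and is not tied to it. What remains is that the usual form does not relax proportionality and no other form is specified.

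The second reply is scale, and it stands. The simulated effects are assumed and strong, and no document gives such effects for any covariate. With about 88 subjects the check would often not reject, and where it did, sampling error would dwarf any difference between Cox and Weibull. A reader might also infer that the study's conclusions are at risk. They are not: protocol 10 describes the study as descriptive and non-confirmative, and no decision rule uses these ratios.

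Third, part of a better answer is already planned: Kaplan-Meier estimates at 1, 3, 6, 9 months and 1 year (SAP 5.2), interval hazards (protocol 10.1.1) and late linearized rates. That makes the repair easy but does not make the Weibull sentence correct.

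Fourth, an early/late split for every covariate would create a new error. Reduced leaflet motion, symptoms and imaging modality are fixed at the CT visit, at least 30 days after discharge or ACT/DAPT discontinuation. A ratio up to day 30 for them conditions on the future, since a subject who died by then has no value. The fix below is limited accordingly.

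**Conclusion.** The concern holds in this form: the fallback in SAP 11.5 and protocol 10.1.2 does not address the failure that triggers it, because a standard Weibull regression is a proportional-hazards model and neither document specifies a form that is not. This rests on algebra, not on simulation settings. The statement that Cox and Weibull return practically the same ratio is illustrative and depends on the assumed hazards in steps 3 and 4.

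The size is modest. It affects secondary, one-covariate-at-a-time descriptive models with few expected events, and only where the check rejects. The primary exact binomial interval and the Kaplan-Meier estimates are untouched.

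**What to change.** Replace the Weibull sentence in SAP 11.5 and record the departure from protocol 10.1.2, with its rationale, in SAP 3.1, which at present declares no change. Protocol 10.4 allows this route without a protocol amendment. When proportionality is rejected:

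- **Covariates known at implant** (age class, gender, ethnicity, risk factors, baseline NYHA, aortic abnormality, regurgitation on intraoperative TEE, concomitant procedure): report separate hazard ratios with 90% CI up to 30 days and after 30 days, only if both covariate groups have events in both periods. For covariates with more than two levels, apply the condition to each level and its reference. The boundary is borrowed from the plan's linearized rates.
- **Otherwise:** report no single ratio, including beside the Kaplan-Meier output of SAP 5.2. Give Kaplan-Meier curves by group and the between-group difference in 1-year freedom from the event with its 90% CI.
- **Covariates determined after implant** (ACT/DAPT status at discharge; reduced leaflet motion, symptoms and imaging modality at the first CT): do not use the early/late split. Start the curves at the date the covariate is determined and state the time horizon, since follow-up from that date is shorter than from implant.

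The cost is a short replacement text and one entry in SAP 3.1; no new data are needed. The downside is wider intervals in each period and no ratio where events are sparse. By step 5, that will be the usual case for the rarer outcomes.

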7.7. UNSCHEDULED VISITS

Unscheduled visits in symptomatic subjects (subjects with symptoms of reduced leaflet function) and any other subjects needing a study related follow-up visit that is not covered by the standard visit schedule. The following items may be captured:

- Subject status
- Physical evaluation (including cardiac rhythm and NYHA functional classification)
- Medications
- Transthoracic echocardiogram (TTE) (if available)
- SAEs

7.8. 2ND CT SCAN VISIT/REDUCED LEAFLET VISIT (AFTER THE 1ST CT SCAN, BUT PRIOR TO 1-YEAR FOLLOW-UP VISIT)

This visit is intended provide a 2nd follow-up 4D CT scan if the 1st CT scan showed reduced leaflet motion. This second CT scan visit is expected at approximately 6-10 months, but prior to 1 year follow-up. This follow-up evaluation shall be conducted in an office, hospital or clinic setting by the PI or his/her designee, at a time designated by the PI.

If the 1st CT scan showed no signs of reduced leaflet motion, a repeat 4D CT is not mandated and will only be done if it becomes clinically indicated. For subjects unable to undergo a contrast CT scan (e.g. inadequate renal function), a TEE may be performed.

The following data listed below shall be collected if this visit is required:

- Subject status
- Physical evaluation (including cardiac rhythm and NYHA functional classification)
- Medications

- Hemodynamic data from TTE examination measured at investigational site (MPG; PPG, EOA, aortic regurgitation with severity and location)
- CT scan with contrast
- TEE only in subjects that are unable to undergo CT scan at the time of follow-up
- Medications
- SAEs

7.9. 1-YEAR FOLLOW-UP VISIT

This visit is intended as a clinic visit at 1 year \pm 1 month after the day of the surgery. Follow-up evaluations shall be conducted in an office, hospital or clinic setting and are to be performed by the PI or his/her designee. **All efforts should be made to ensure that the subject comes to the clinic.**

The following data listed below shall be collected:

- Subject status
- Physical evaluation (including cardiac rhythm and NYHA functional classification)
- Medications
- Hemodynamic data from TTE examination measured at investigational site (MPG; PPG, EOA, aortic regurgitation with severity and location)
- Medications
- SAEs

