18.6 VISIT WINDOWS

Measurements will be assigned to visits according to the windows allowed in the Protocol and reported in Figure 2. These are defined in Section 5.4 and resumed below:

- Pre-implant/implant: during and after successful implant.
- Hospital Discharge: ≤30 days post-implant.
- ACT/DAPT discontinuation visit: 1-6 months post-implant.
- First CT scan visit: ≥30 days (+ 60 days) after discharge (for subjects discharged off ACT/DAPT) or after ACT/DAPT discontinuation (for subjects discharged on ACT/DAPT).
- Second CT scan visit: after the first CT Scan and 6-10 months post-implant.
- 1 year visit: 1 year ± 1 month post-implant.

Figure 2: Visit Window Guide

Visit Name	Calculate from:	Window Start Day	Window Stop Day
Pre-Implant / Implant Data	Enrollment date	- 90	0
Hospital Discharge (completed prior to actual discharge)	Implant date	0	30
ACT / DAPT Discontinuation or Planning Visit	Implant date 90 days after Implant date preferred	30	180
1st CT-scan Follow-up Visit (no ACT/DAPT)	Hospital Discharge date 30 days after Hospital Discharge preferred	30	90
1st CT-scan Follow-up Visit (DC on ACT/DAPT)	ACT / DAPT Discontinuation date	60	240
2 nd CT-scan (if needed) A minimum of 6 weeks after 1 st CT-scan	Implant date	180	300
1 year follow-up	Implant date	335	395

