ENR population	 SCR flag= "Yes" and DXSTDAT2 not missing ("Implant Surgical Details" e-CRF) and existing Enrolled Date
SAF population	 ENR flag= "Yes", and DXPERF= "Yes" ("Implant Surgical Details" e-CRF)
PP population	As reported in the Believe Risk Based Study Management Plan.
Time to study	"Implant Surgical Details" e-CRF and "Study Termination" e-CRF
termination (months)	[DSSTDAT – DXSTDAT2 + 1] / 30.4375

COPYRIGHT LIVANOVA. ALL RIGHTS RESERVED. MAY NOT BE REPRODUCED WITHOUT PERMISSION. ALL HARD COPIES SHOULD BE CHECKED AGAINST THE CURRENT ELECTRONIC VERSION WITHIN MASTERCONTROL PRIOR TO USE AND DESTROYED PROMPTLY THEREAFTER. ALL HARD COPIES ARE CONSIDERED UNCONTROLLED DOCUMENTS.

LN-GLB-CLN-TEM-0033 rev1 Page 40 of 42

Time to event	"Implant Surgical Details" e-CRF
(months)	[Even date – DXSTDAT2 + 1] / 30.4375 Subjects ongoing and who are free from event at the analysis cutoff date will be censored at the analysis cut-off date. Subjects who have discontinued without an event will be censored at the date of discontinuation.
Age at Enrollment (years)	"Demographics" e-CRF and "Inclusion/Exclusion Criteria" e-CRF Age= [ICFDAT - BRTHDAT + 1]/365.25 As only month and year of birth are reported in the CRF, 1 st day of the month will be used for birth date.
Change from baseline	Test Value at Visit X - Baseline Value

Where

ACTDIDAT = "Date Subject Discontinued ACT/DAPT Therapy"

BRTHDAT= "Date of Birth"

CPAETERM= "Complications/Please specify if any of the following intraoperative complications occurred. /AE Term"

CPYN= "Was concomitant procedure performed?"

DIMODEL= "Valve Model"

DSDECOD= "Reason for Termination"

DSSTDAT= "Date of Study Termination"

DVDECOD= "Deviation Description"

DVICSPEC= "If Informed Consent, specify reason"

DXPERF= "Was the implant successful?"

DXSTDAT2 = "Date of Implant"

ICFDAT = "Informed Consent Date"

IEYN= "Met All Eligibility Criteria?"

COPYRIGHT LIVANOVA. ALL RIGHTS RESERVED. MAY NOT BE REPRODUCED WITHOUT PERMISSION. ALL HARD COPIES SHOULD BE CHECKED AGAINST THE CURRENT ELECTRONIC VERSION WITHIN MASTERCONTROL PRIOR TO USE AND DESTROYED PROMPTLY THEREAFTER. ALL HARD COPIES ARE CONSIDERED UNCONTROLLED DOCUMENTS.

LN-GLB-CLN-TEM-0033 rev1 Page 41 of 42

IMGTYPE= "Specify the imaging modality currently being used for the subject"

MHCVDAT = "If Myocardial Infarction, date"

MHSTDAT3= "If Stroke, date"

NY= "No/Yes"

SCDISCYN= "Was the subject discharged on anticoagulant and/or dual platelet therapy?"

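### SAP 11.5 runs Kaplan-Meier on one scheduled scan per subject, so the curve's tail follows scan timing; its time origin and censoring rules also conflict

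*SAP*

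**What the plan says.** The last paragraph of SAP 11.5 plans an additional analysis of the time from stopping ACT/DAPT to the primary endpoint, up to 1 year post-implant. Its rules come from several places.

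- **Scale:** "Kaplan-Meier estimates and plots of time to event after implant will be produced as in" SAP 5.2. The derivation table in SAP 18.13 also counts time to event from the implant date.
- **Entry and exit:** "Subjects will be included in the analysis starting from their stop date of ACT/DAPT until the first evaluation of leaflet motion".
- **Censoring:** SAP 5.2, to which the paragraph refers, says "Subjects ongoing and who are free from event at the analysis cut-off date will be censored at the analysis cut-off date". SAP 18.13 repeats this.
- **Output:** SAP 5.2 asks for "the respective number at risk and the Kaplan-Meier estimates at time points 1 month, 3 months, 6 months, 9 months and 1 year", plus the median with its 90% CI.
- **Scans:** after a normal first scan, Protocol 7.8 says "a repeat 4D CT is not mandated and will only be done if it becomes clinically indicated". SAP 10.5 agrees.
- **First-scan window for subjects discharged on ACT/DAPT:** the text of SAP 18.6 gives 30 days plus 60 after discontinuation. The Visit Window Guide in the same section gives days 60 to 240.

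No interval-censored or current-status method is named.

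**The concern.** A single scan shows whether reduced motion is present on that day. It does not show when it began, so these are current-status data. Kaplan-Meier needs an observed event time, and here it is given the appointment date.

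Two things follow. First, if negatives leave at their own scan, the number at risk falls as the window closes. A positive found when k subjects remain cuts the curve by 1/k: a tenth when ten remain, half when two remain, all of it when one remains. The curve then climbs late even if risk does not depend on time off therapy. Second, the origin (implant or stop date) and the censoring point (first scan or cut-off) are each given two ways, so two programmers could follow the SAP and report different results.

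Reduced leaflet motion off therapy is the study's subject. A curve ending near 35% beside a primary estimate near 10% would invite the reading that risk rises with time off therapy.

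**Working it through.** **Inputs.** Evaluable n = 75 and a sample proportion below 10% (SAP 2.3); 90% two-sided intervals (SAP 5.1); first-scan windows of 30-90 and 60-240 days after stop (SAP 18.6); reporting times 1, 3, 6, 9 and 12 months (SAP 5.2). *Assumed, because the documents do not say:* positivity of 10% or 5% unrelated to scan day, scan days spread evenly over whole days, no dropout, and n = 40 to 75 (the number with a stop date is not given and is below the full evaluable set).

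**The plan's own figure.** There is none for this curve. The precision statement reproduces: the largest count below 10% of 75 is 7, and 7/75 = 9.3% has an exact 90% CI of 4.46% to 16.82%, width 12.35%, under 13%. Also 75/0.85 = 88.2.

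**Formula for the inflation.** Order the scans and ignore ties. When k remain, the next subject out is positive with probability p and multiplies the curve by (1 - 1/k); otherwise it is unchanged. The expected factor is 1 - p/k, so

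expected final incidence = 1 - product over k = 1..n of (1 - p/k).

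With n = 75, p = 7/75 gives 37.2% and p = 0.10 gives 39.3%. At p = 0.10 the last five scans alone contribute 0.90 x 0.95 x 0.967 x 0.975 x 0.98 = 0.79. Ties on whole-day dates lower the total somewhat.

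**Simulation, 10% positivity, n = 40 to 75.** Ranges cover the sample sizes and repeated runs.

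| Reading | Mean final 1-KM | Median |
|---|---|---|
| Stop-date origin, scans days 30-90, negatives out at scan | 33-36% | 26-30% |
| Stop-date origin, scans days 60-240, negatives out at scan | 35-38% | 27-32% |
| Implant origin, entry at stop (assumed even over days 30-180), scans 30-90 days later | 39-44% | 32-37% |
| Negatives censored at cut-off | about 10% | about 10% |

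- The 5th percentile is about 5-11%. The 95th is 100%, except about 80% for days 30-90 at n = 75.
- With exactly 7 of 75 positive, the means are 34.5% (days 30-90) and 36.9% (days 60-240).
- At 5% positivity the stop-date means are 18-21% and the medians 11-14%.
- The curve reaches 50% in about 20-24% of trials, so the requested median is usually not estimable.

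**Where it shows.** From the stop date with days 30-90, nobody is at risk at 3 months, so the inflated value stands from there. With days 60-240 the curve averages 2% at 3 months and 10.7% at 6 months (about 32% still at risk); the inflation appears at 9 and 12 months, with nobody at risk.

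**Cut-off censoring.** With 7/75 and days 30-90 the curve reads 2.5%, 4.8%, 7.1% and 9.3% at days 45, 60, 75 and 90. That is the scan calendar multiplied by 9.3%. The plateau is the crude proportion, but time without a scan is counted as event-free.

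**Origin.** A subject who stops on day 90 and is scanned on day 120 after implant has 31/30.4375 = 1.0 month from stop and 121/30.4375 = 4.0 months from implant.

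**The case against.** The strongest reply is that SAP 5.2 also requires the number at risk. From a stop-date origin, the values of 33-38% fall only at listed times where that number is zero. Kaplan-Meier is conventionally left undefined after a last censored observation, so many tables would show a blank. This stands for the table under that origin, but not for the plot, whose tail still climbs. Under implant origin with delayed entry, inflation reaches listed times with subjects at risk: about 15% at 6 months for scans 30-90 days after stop, and about 25% at 12 months for scans 60-240 days after stop (about 4 of 75 at risk), against a true 10%.

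Second, the two origins can be read together as delayed entry on an implant scale, and a rule specific to one analysis normally overrides a general default. Both readings are possible. The SAP states neither, delayed entry does not estimate time off therapy (the paragraph's aim), and the reference to SAP 5.2 brings in the competing censoring rule.

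Third, the size depends on the scan calendar. Weekly slots across days 30-90 reduce the mean to about 25%. That is fair: the figures illustrate the effect and do not predict it. A mean of 25% against a true 10% is still wrong in the same direction.

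Last, this is one additional analysis in a study declared descriptive. That limits the severity but does not make the method suit the data.

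**Conclusion.** The point holds. Kaplan-Meier does not suit one scheduled look per subject, and the paragraph leaves origin and censoring open between rules that give different answers: about 10% or about 35% when the true value is a flat 10%. The size rests on the assumed positivity, evenly spread scan days and n = 40 to 75; the mechanism does not. The primary exact-binomial estimate (SAP 10.4) is untouched and no decision rule uses the curve. The consequence is a misleading secondary figure that should be corrected before analysis.

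**What to change.** In SAP 11.5:

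1. Delete the Kaplan-Meier estimates, plot and median for this endpoint.
2. Define one time variable, days from ACT/DAPT stop to first scan. Remove the reference to time after implant, and state that the cut-off censoring rule does not apply.
3. Report the crude proportion with its exact 90% CI, and a logistic model of the first-scan result on those days with a 90% CI. Univariate logistic models are already planned in SAP 11.4.
4. State that subjects discharged off ACT/DAPT, and those who never stop, have no stop date and are not included. Counting the first group from discharge would be a different time variable and would need its own description.
5. If a nonparametric current-status estimate is shown, do not report its tail. It is also biased upward: at the last scan the mean is 26-29% and the median 18-20%, against a true 10%.

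The two first-scan windows in SAP 18.6 must also be reconciled, since they determine the range of the time variable.

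The cost is SAP wording and a different model on the same data, with no added visits or scans. The drawback is imprecision with few events. The 90% CI for the odds ratio per 30 days spans about a factor of 3-5 either way for days 30-90, and 1.5-1.7 for days 60-240. At n = 40 the model cannot be fitted reliably in about 9% of simulated trials; in that case report only the crude proportion.
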